This is a pilot study and is not powered to test the effect of the HELP PD Vets intervention on any outcome. The sample size of 50 for this pilot study was selected to provide reasonably tight estimates of the treatment effect, allowing us to estimate treatment differences in continuous outcomes to within ± 0.6 SD with 95% confidence (assuming a dropout of 16%). Retention can be estimated to within $\pm 14\%$ and successful adherence within the intervention to within $\pm 20\%$. The estimates obtained in this study will be used to design a fully powered randomized controlled trial assessing the effect of the HELP PD Vets intervention on blood glucose. Estimates of the variability of the outcome measures obtained in this study will be used to determine the required sample size in the subsequent trial. Effect estimates will inform us if desired effects are feasible. Estimates of retention and adherence will be used to modify the sample size to account for dropouts and poor adherence. Estimates of the participation and accrual rates will be used to judge the feasibility of the subsequent trial given the required sample size relative to patient availability and our ability to recruit them into our trial.

IV. Interventions and Interactions

a. Intensive Lifestyle Intervention

The intensive lifestyle intervention used in HELP PD was a modification of the DPP core curriculum adapted for use in groups. The 16-session core curriculum used in DPP, covering key concepts related to energy balance, nutrition, and physical activity, was expanded to include regular sessions focused on group problem-solving of barriers and issues specific to the members and to incorporate presentations from local community groups on topics relevant to weight-loss and healthy living (exercise resources, food shopping, etc.) The same intervention will be used in HELP PD Vets and will target decreased caloric intake (reduction of 500-1000 kcal/day) and increased caloric expenditure through moderate intensity physical activity (goal ≥ 180 min/wk). The primary objective will be to produce a total weight loss of 5-7% from baseline during the 6-month intervention. A DVD series was developed in HELP PD to standardize this core content, improve fidelity of intervention delivery, and to allow the CHWs to focus on group facilitation and problem-solving. This DVD series will also be used in HELP PD Vets.

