There will be 24 sessions delivered over the course of 6 months; materials consist of CHW lesson plans, participant workbooks, and the DVD series. These materials will be adapted for use in HELP PD Vets and

may include information on mental health resources available to Veterans for common illnesses like depression and post-traumatic stress disorder and modifying physical activity recommendations for Veterans with limited mobility. We will conduct an initial round of modifications to the materials prior to training community health workers and will modify the materials again based on feedback received during that training. Final adaptations to the materials will be made (for the subsequent larger trial) based on feedback collected from the participants at their 6-month close out visit.

The training programs for staff and lay personnel will be adapted from HELP PD and designed with the understanding that staff delivering diabetes education services as part of a PACT in the Kernersville Health Care Center will be trained by investigators and staff from Wake Forest School of Medicine to screen and enroll participants, recruit and train community health workers, and administer, implement, and monitor the HELP PD Vets 6-month weight-loss program. The training program will focus on study specific material and consist of a) study protocol; b) program philosophy, goals, and procedures; c) weight loss (energy balance); d) physical activity basics; e) group facilitation; f) cognitive-behavioral principles; g) participant monitoring; and h) use of the study website for data entry.

Table 1. Weekly Session Topics from HELP PD

Session #	Session Title
1	Welcome to HELP PD
2	Nutrition 101
3	Physical Activity 101
4	Footwear
5	Troubleshooting
6	Calorie Balance
7	Mindfulness
8	Portion Sizes
9	Troubleshooting
10	Community Exercise/Nutrition Resources
11	Problem Solving
12	Physical Activity Hands On
13	Troubleshooting
14	Emotions and You
15	Healthy Eating
16	Stretching/Injury Prevention/Strength Training
17	Troubleshooting
18	More about Healthy Eating
19	Food shopping/eating out
20	Creating an Environment for Success
21	Troubleshooting
22	Wt. loss maintenance
23	Preparation for Independence
24	Transition

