We will conduct a preliminary cost estimation of HELP PD Vets. Direct medical cost is a close proxy for what the intervention delivery would cost a large healthcare provider, such as the Veteran's Administration, a hospital, or insurance company. These direct costs will include the implementation of the lifestyle intervention and side effects of the intervention. We will estimate cost by relying on records of personnel and material costs and records of the number of participants attending intervention sessions; this information will be jointly collected by Wake Forest and staff from the Kernersville Health Care Center. Since this is a feasibility pilot study, we will not attempt the expensive and labor-intensive process of collecting and analyzing all data on cost, outcomes and efficacy associated with this trial from all possible standpoints, as would be required in a full-scale cost-effectiveness analysis. We will propose such an analysis in the full-scale R18 study.

i. Intervention evaluation

Participants randomized to the lifestyle intervention will be asked to complete a brief, anonymous evaluation at the conclusion of the 6-month close-out visit. This evaluation will capture qualitative data on the conduct of the intervention, participants' interaction with members of the study team, and each

participants' experience in the weight-loss components of the study. The data collected on this evaluation will not be linked to study-related process or outcome data as no ID number, acrostic, or other identifier will be collected. Prior to completing the survey, participants will be provided with a cover letter explaining the purpose of the evaluation and explaining that completion is voluntary. Participants will be provided the opportunity to ask questions about the evaluation and can refuse to complete it at their discretion. The data collected from this evaluation will inform intervention conduct and design in a larger trial.

VI. Analytical Plan

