This feasibility study is designed to provide useful pilot information that can be used subsequently to develop a grant application to translate the HELP PD intervention into the VA healthcare system. Specifically, we will assess our ability to recruit Veterans, obtain estimates of adherence to the intervention and retention to the study, and obtain estimates of the means and standard deviations of outcome measures such as weight loss, waist circumference, BMI, self-reported levels of physical activity, and caloric intake. For recruitment, we will estimate the proportion of referred patients who are eligible for the study and the proportion of eligible patients who agree to participate. For adherence, we will estimate the proportion of intervention sessions attended. For retention, we will estimate the proportion of participants who complete the study. For the continuous outcome measures, we will estimate the means and standard deviations at each measurement time and the correlation over time. These data are necessary for developing larger scale VA translational efforts. Participants will be assigned to HELP PD Vets or EUC with equal probability using variable length permuted block randomization through a web-based data entry system. Estimates of intervention efficacy will be obtained using the 'intent to treat' approach, in which all randomized participants will be used in the analyses, regardless of protocol adherence. Data will be collected at baseline and 6-months at visits conducted by appropriate medical staff at the VA.

Missing Data

In longitudinal trials, it is likely that some data will be missing due to missed forms, missed visits, or patient drop-out. We will minimize missingness by: 1) using incentives and sending multiple reminders, 2) providing multiple methods for data collection (paper, phone), and 3) attempting to contact participants with missing items. Additionally, multiple imputation methods will be used to assess the sensitivity of our conclusions to assumptions regarding the missingness.

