Descriptive statistics (means, standard deviations, frequencies, etc.) will be presented for pretreatment participant characteristics and the outcome measures mentioned above. Each of the outcomes will be analyzed and reported separately. Exact confidence intervals will be provided for the estimated proportions. Analysis of covariance will be used to obtain estimates of the intervention effect for each outcome and to obtain adjusted estimates of the variability of these outcomes. Least squares means and 95% confidence intervals will be provided for each outcome, stratified by intervention, and for the difference between the treatment arms. Subsequent models will include additional covariates such as age and gender. Regression diagnostics and residual plots will be used to find appropriate

transformations for the variables in the models to satisfy the linearity, homogeneity of variances, and normality assumptions. Limited (because of our small sample size) exploratory analyses will be done to determine if the treatment effect differs for different levels of the covariates (e.g., by including intervention by covariate interactions in the model) to see if the subsequent fully-powered trial should be conducted in particular subsets (e.g. specific age ranges) of participants. Logistic regression will be used to determine which participant characteristics are associated with the binomial outcomes such as retention and successful adherence (in the intervention arm).

Data Management and Quality Control

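### Exact binomial intervals do not suit the session-attendance measure of adherence; it needs a participant-level interval

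*Combined protocol and SAP*

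**What the plan says.** Section VI (Analytical Plan) lists the feasibility proportions: eligible among those referred, agreeing among those eligible, completing the study and, for the intervention, attendance: "For adherence, we will estimate the proportion of intervention sessions attended". The same section then sets one interval method for all of them: "Exact confidence intervals will be provided for the estimated proportions". It makes no exception for attendance. Section IV.a gives the schedule: "There will be 24 sessions delivered over the course of 6 months".

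A second form of adherence also appears. Section III.d (Sample Size) promises "successful adherence within the intervention to within" ±20%, and section VI plans logistic regression for "binomial outcomes such as retention and successful adherence (in the intervention arm". That is a yes/no outcome per person. No section says what share of sessions counts as success.

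Section III.d gives the use of the results: "Estimates of retention and adherence will be used to modify the sample size to account for dropouts and poor adherence".

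**The concern.** For three of the four listed proportions, each person contributes one yes/no, so a binomial count is the right model. Attendance is different, because a person contributes up to 24 sessions. Someone who attends regularly tends to keep doing so, and someone who leaves misses everything afterwards. An exact interval on total sessions attended treats these as independent trials and is too narrow.

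Estimating adherence is one of the pilot's stated purposes, and the estimate feeds the next trial's sample size. An interval that counts sessions as though they were people would make attendance look much better known than about 25 participants allow.

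**Working it through.** **Inputs from the documents.** 50 participants, 1:1 allocation, so about 25 in the intervention arm; 24 sessions; 95% confidence; 16% dropout. **Assumed, not in the documents:** the attendance rate and the within-person correlation (ICC).

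**1. The plan's own figure.** Half-width at p = 0.5 is 1.96 × √(0.25/n).
- n = 25 people: 1.96 × √(0.25/25) = 0.196, the stated ±20%. The exact interval for 12/25 is 27.8–68.7%, or ±20.4 points.
- n = 600 person-sessions: 1.96 × √(0.25/600) = 0.040.

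So ±20% belongs to the yes/no outcome in 25 people, not to session attendance.

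**2. The exact interval on attendance.** With 25 × 24 = 600 person-sessions and 75% attended (450), the Clopper–Pearson limits are 71.3% and 78.4%, about ±3.5 points.

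**3. Effect of within-person correlation.** The design effect is 1 + 23 × ICC, and the effective number of sessions is 600 divided by it. The participant-level half-width is about t(24) × √[p(1−p)(1 + 23 × ICC)/24] / √25. At p = 0.75 and ICC 0.05 this is 2.064 × √(0.1875 × 2.15/24)/5 = 0.053. Coverage comes from beta-binomial simulation (25 people, 24 sessions, 60,000 runs, mean attendance 75%):

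| ICC (assumed) | Design effect | Effective sessions | Pooled exact coverage | t half-width (points) | t coverage | t width / pooled width |
|---|---|---|---|---|---|---|
| 0.05 | 2.15 | 279 | 83.3% | 5.3 | 94.6% | 1.50 |
| 0.10 | 3.30 | 182 | 73.7% | 6.5 | 94.6% | 1.85 |
| 0.20 | 5.60 | 107 | 60.4% | 8.5 | 94.3% | 2.42 |
| 0.30 | 7.90 | 76 | 52.9% | 10.2 | 94.0% | 2.89 |
| 0.40 | 10.20 | 59 | 47.0% | 11.5 | 94.0% | 3.29 |

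Pooled coverage changes little with the mean: 82.6% to 46.5% at 60% attendance and 83.7% to 47.1% at 90%. In a separate run with ICC near zero (0.001), at 50% and 70% attendance, it is about 95%, so the correlation is the cause.

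**4. Is such a correlation plausible?** Section III.d plans on dropout ("assuming a dropout of 16" per cent). Assume that each person leaves with probability 0.16 after session k, that sessions after leaving count as missed, and that everyone attends 85% while enrolled with no other differences between people. For k = 6, the two true rates are 0.85 and 0.85 × 6/24 = 0.2125.
- Mean: 0.85 − 0.16 × 0.6375 = 0.748.
- Between-person variance: 0.16 × 0.84 × 0.6375² = 0.0546.
- Within-person variance: 0.84 × 0.1275/24 + 0.16 × 6 × 0.1275/24² = 0.0047.
- Design effect: 0.0593 / (0.748 × 0.252/24) = 7.55, so the implied ICC is 6.55/23 = 0.285.

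| Leaves after session | Implied ICC | Pooled coverage | t coverage |
|---|---|---|---|
| 6 | 0.285 | 52.3% | 92.3% |
| 12 | 0.135 | 68.2% | 93.2% |
| 18 | 0.034 | 86.7% | 94.4% |

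With dropout spread uniformly over the sessions, and 75%, 85% or 95% attendance while enrolled, pooled coverage is 69.2%, 59.7% or 46.6%, and t coverage is 91.3%, 90.2% or 88.5%.

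**5. The estimate itself.** With a fixed denominator of 24, total sessions attended / 600 equals the mean over people of (attended / 24). Only the interval differs.

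**The case against.** The strongest reply is that the plan never proposes to pool sessions. Its participant-level figures (the ±20%, the logistic regression) suggest that the authors were thinking of people, and the sentence on exact intervals could be meant only for count-based proportions. This stands in part: pooling is a risk created by the wording, not a stated analysis. But the ±20% and the regression concern the yes/no outcome. The attendance measure sits in the list to which the sentence applies, and no participant-level summary of it is given.

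One could instead apply an n = 25 binomial interval to the mean attendance. That needs a non-integer count (75% of 25 is 18.75), so it is an unlikely choice. It would also err the other way: about ±18 points with over 99.9% coverage.

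A reader might infer from section V.h, which relies on "records of the number of participants attending intervention sessions", that only pooled counts will exist. The documents do not support that. Those records are for costing, while the data management text in section VI describes adherence reporting and tracking by participant. A reader might also extend the point to clustering by group and to the ±0.6 SD for treatment differences. That is a different quantity, and the number of groups is not stated.

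Finally, section III.d says that estimates, not interval limits, will adjust the next sample size, and the estimate does not change. That is right, and it limits the harm to overstated precision.

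**Conclusion.** The concern holds for one measure. An exact binomial interval is unsuitable for session attendance and suitable for the other listed proportions. The ±20% for binary successful adherence stands at n = 25. If the rule is applied to attendance as worded, a nominal 95% interval covers about 83% down to 47% at an assumed 75% attendance and ICC of 0.05 to 0.4. The size rests on those assumptions. The direction does not: positive within-person correlation makes the pooled interval too narrow for its model.

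It would go too far to say that the plan will pool sessions, that its adherence estimate is biased, or that its stated precision for adherence is wrong. The documents support none of these.

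**What to change.** Add an exception to the interval sentence in section VI:
- For each person randomised to the intervention, compute the percentage of the 24 sessions attended, counting sessions after dropout as not attended.
- Report the mean and SD with a participant-level t or bootstrap 95% interval, with and without the make-up sessions described in section IV.a.
- Keep exact intervals for the one-per-person proportions: eligible, agreeing, retained and successfully adherent. Fix the cut-off for successful adherence before data are seen, and tie the ±20% to that outcome.

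The cost is two or three sentences and a few lines of code, with no change to sample size or conduct. Since tracking by participant is already described, the data should be available.

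The interval will be about 1.5 to 3.3 times as wide as a pooled one, and the t interval is not perfect. Its coverage can fall to about 89–92% when dropout is spread over the sessions (pooled: about 47–69% in the same runs), and to about 90% at 90% attendance with ICC 0.4 (pooled: 47%). A percentile bootstrap gave 93–94% at 75% attendance, so it is a reasonable alternative but not clearly better.
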